## Study endpoints and sample size calculation

The primary end point of our study is the comparison of CAT-induced MPA measured by LTA between vorapaxar plus DAPT and vorapaxar plus clopidogrel. We hypothesize that vorapaxar in addition to single antiplatelet therapy with clopidogrel will be non-inferior to vorapaxar in addition to DAPT with aspirin and clopidogrel in MPA after 30±5 days of treatment in both DM and non-DM patients. Under the assumption of 0 difference in mean CAT-induced MPA between vorapaxar plus clopidogrel and vorapaxar plus DAPT and a common standard deviation of 13%, a sample size of 28 patients per group allows for the 95% confidence interval (CI) to stay within  $\pm$ 10% with a 80% power and alpha=0.025. Considering the two groups (DM and non-DM), a total of 56 patients with valid primary end point data will need to be included. Assuming up to 40% rate of invalid results due to haemolysis or drop-out, up to 79 patients will need to be enrolled. Noninferiority will be assessed using a 95% CI of the difference in mean MPA between the 2 arms. As there are no preliminary data in this setting, the 10% non-inferiority margin was arbitrarily defined. Mean values of platelet aggregation and variability were estimated based on previous data of vorapaxar in addition to DAPT with aspirin and clopidogrel [24]. This approach is in agreement with recommendations for pilot investigations [28].

Other objectives will include the comparisons between DM and non-DM patients of all PD parameters measured by multiple assays, and the comparisons between levels of platelet inhibition achieved by DAPT (baseline therapy) versus levels achieved by antiplatelet therapy including vorapaxar. The effects of additive inhibition of the thrombin-mediated platelet activation pathway, with or without aspirin therapy, on serum thromboxane levels will also be evaluated.

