in Myocardial Infarction 50) trial [13]. In particular, the trial showed that the use of vorapaxar in addition to standard antiplatelet therapy was effective in the secondary prevention of recurrent thrombotic events (cardiovascular death, MI, or stroke) in patients with previous atherothrombosis, particularly those with prior MI and PAD, albeit at the cost of increased bleeding [13,14].

Patients with DM are known to be at increased risk of recurrent atherothrombotic events, which translates into worse outcomes, despite the use of standard of care therapy [4,15]. This is in part due to the hyperreactive platelet phenotype with upregulation of multiple platelet signaling pathways, including thrombin, which characterizes patients with DM [4]. Importantly, increased platelet reactivity may account for inadequate response (i.e. reduced platelet inhibitory effects) to oral antiplatelet agents, including the  $P2Y_{12}$  receptor antagonist clopidogrel, contributing to worse outcomes [4]. Notably, in DM patients and prior MI included in the TRA 2P trial, vorapaxar reduced the primary composite end point at 3 years by 27% (p=0.002), and led to a greater absolute risk reduction (absolute risk difference: -3.50%) compared with those without DM (absolute risk difference: -1.36%) with a number needed to treat of 29 [16]. The benefit of vorapaxar was also consistent in patients with PAD, although no specific subgroup data are available based on DM status [17]. Therefore, patients with DM, characterized by diffuse atherothrombotic disease manifestations and enhanced risk of ischemic recurrences, seem particularly attractive for treatment with vorapaxar. However, to date the PD effects of vorapaxar in patients with DM, as well as the comparative effects of DM versus non-DM patients has not yet been explored.

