## **Study Rationale and aims**

Despite the encouraging clinical findings from TRA-2P and the potential for an uptake of vorapaxar in daily practice, there is limited data on the PD effects of vorapaxar as an add-on therapy in key high-risk settings, such as prior MI or PAD patients with DM, where enhanced platelet

inhibition by means of PAR-1 blockade, may be more clinically beneficial. Further, given the length of the TRA-2P trial (median follow-up of 30 months), many patients were enrolled in the trial while on standard DAPT with aspirin and clopidogrel, but then interrupted one antiplatelet agent as per standard of care [13]. Although most patients discontinue clopidogrel therapy and continue aspirin, current trends in clinical practice are seeing many patients discontinue aspirin and maintain clopidogrel, which provides more comprehensive platelet inhibition compared with aspirin [18]. Hence, the role of vorapaxar as part of a dual antithrombotic treatment regimen combined with clopidogrel (and stopping aspirin) represents another important area of clinical interest, in order to maximize ischemic protection while reducing the risk of bleeding. Further, the comparative PD effects of vorapaxar in addition to different combination of antiplatelet therapy in patients with DM versus those without DM is currently unknown. A comprehensive understanding of the PD effects of vorapaxar as an add-on therapy will thus be informative to the practicing clinician. Therefore, the aim of the proposed investigation is to assess the PD effects of vorapaxar in addition to DAPT with aspirin and clopidogrel as well as to antiplatelet therapy with clopidogrel, in the setting of post-MI or PAD patients with and without DM.

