### Statistical analysis plan

Categorical variables will be expressed as frequencies and percentages. Continuous variables will be presented as mean ± SD or median [IQR]. Continuous variables will be analyzed for normal distribution with the Kolmogorov-Smirnov test. Comparisons between categorical variables will be performed using two-tailed Fisher's exact test or the Pearson's chi-square test. Student's t test, Mann-Whitney U-test and Wilcoxon test will be used to compare continuous variables when appropriate. An analysis of covariance (ANCOVA) method with a general linear model, using baseline variables significantly different between groups as covariates, will be used to evaluate the overall difference between groups and all between-groups comparisons, in line with other PD studies [25]. Student's t test or Wilcoxon test will be used to evaluate intragroup comparisons. Non-inferiority will be assessed using a 95% CI of the difference in mean MA between vorapaxar plus prasugrel/ticagrelor and vorapaxar plus DAPT.

A p-value of <0.025 will be considered to be statistically significant for the non-inferiority analysis. A 2-tailed p value of < 0.05 is considered to indicate a statistically significant difference for all the other analyses performed. Statistical analysis will be performed by our group using SPSS v22.0 software (SPSS Inc. Chicago, IL).

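### No planned analysis contrasts the change on vorapaxar between the DM and non-DM cohorts, so a pre-existing difference in platelet reactivity could be mistaken for a different drug effect

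*Combined protocol and SAP*

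**What the plan says.** **The question.** Study Rationale and aims describes as unknown the "comparative PD effects of vorapaxar in addition to different combination of antiplatelet therapy in patients with DM versus those without DM". The Summary and Background and Significance name the same gap.

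**The planned comparisons.** Study endpoints and sample size calculation lists two relevant objectives. The first sets the cohorts against each other: "Other objectives will include the comparisons between DM and non-DM patients of all PD parameters measured by multiple assays". The second, which is not said to be contrasted between cohorts, sets baseline therapy against the vorapaxar regimens: "the comparisons between levels of platelet inhibition achieved by DAPT (baseline therapy) versus levels achieved by antiplatelet therapy including vorapaxar".

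**The methods.** Under Statistical analysis plan, between-group work is done by ANCOVA, "using baseline variables significantly different between groups as covariates, will be used to evaluate the overall difference between groups and all between-groups comparisons". Within groups, "Student's t test or Wilcoxon test will be used to evaluate intragroup comparisons". There is no change score, cohort-by-visit interaction or repeated-measures model, and the text does not say whether the baseline PD value counts as a candidate covariate.

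**The design.** Under Research Design, cohorts are formed by DM status, and PD samples are taken on DAPT before vorapaxar, after triple therapy and after dual therapy. Background and Significance expects a starting difference. It attributes the higher risk in DM to platelet biology: "This is in part due to the hyperreactive platelet phenotype with upregulation of multiple platelet signaling pathways, including thrombin".

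**The concern.** A drug effect in this design is a change from the DAPT baseline. Whether that effect differs by DM status is therefore a difference between cohorts in within-patient change. The plan tests the two halves separately, cohort against cohort and visit against visit, and never joins them.

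The protocol itself predicts the complication. If platelets in DM are more reactive before vorapaxar, including in the thrombin pathway that vorapaxar blocks, they can remain more reactive on vorapaxar even when the drug does exactly the same in both cohorts. A significant cohort difference on treatment would then show that DM platelets are more reactive, which the Background already takes as known. It would not show that vorapaxar acts differently in DM, which is what the study set out to learn. The sample that could separate the two is collected, but no named analysis uses it for this purpose.

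**Working it through.** **Inputs from the documents.** SD 13 points and 28 patients per group (sample size section); two-sided 0.05 for all analyses other than non-inferiority (Statistical analysis plan).

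**Assumed, because the documents give no figure.** A DM offset d of 5, 8 or 10 points, equal at baseline and on vorapaxar; a within-patient correlation r of 0.3, 0.5 or 0.7; an equal additive drug effect in both cohorts; normal data.

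**Step 1: the plan's own figure.** For the primary endpoint with margin 10, n = 2 × 13² × (1.96 + 0.842)² / 10² = 26.5, so 27 per group. The t-based version gives power of 79.2% at 27 and 80.7% at 28. The stated 28 is reproduced. No power is given for DM versus non-DM.

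**Step 2: what each comparison estimates when the drug effect is equal.**
- Levels on treatment: d.
- Levels adjusted for baseline: d − r × d = d(1 − r), because with equal SDs the regression slope is r. At d = 10 and r = 0.3, 7 points remain.
- Difference in change: d − d = 0.

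**Step 3: how often the covariate rule acts.** With 28 per cohort, a true 5-point offset is significant at baseline in only about 29% of trials. In the rest, the rule leaves the baseline value out.

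**Step 4: simulation.** 20,000 trials per scenario, 28 per cohort. The table gives the percentage of trials with p<0.05 for DM versus non-DM although the drug effect is equal. The plan's rule is read favourably: the baseline PD value is a covariate if it differs at p<0.05, and otherwise levels are compared.

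| Analysis | d = 5 | d = 8 | d = 10 |
|---|---|---|---|
| Plan's rule, r = 0.3 | 22 | 40 | 51 |
| Plan's rule, r = 0.5 | 18 | 30 | 37 |
| Plan's rule, r = 0.7 | 13 | 21 | 24 |
| Baseline always adjusted, r = 0.7 to 0.3 | 9–17 | 15–35 | 20–48 |
| Difference in change, any r | 5 | 5 | 5 |

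A repeat with 60,000 trials per scenario agreed to within about one percentage point.

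**Step 5: precision of the change contrast.** The SD of change is 13 × √(2(1 − r)): 15.4, 13.0 and 10.1 at r = 0.3, 0.5 and 0.7. The difference detectable with 80% power is (1.96 + 0.842) × SD × √(2/28): 11.5, 9.7 and 7.5 points. For levels it is 9.7 points.

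**Step 6: dependence on scale.** Suppose instead that vorapaxar removes the same 40% of aggregation in both cohorts (an assumption). A 10-point offset then becomes 6, and the changes differ by 0.4 × 10 = 4 points. The standard errors are 4.11, 3.47 and 2.69, and the change contrast reaches p<0.05 in about 16%, 20% and 31% of trials at r = 0.3, 0.5 and 0.7. The baseline-adjusted comparison would be left with 6 − 10r = 3, 1 and −1 points.

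**The case against.** **The plan does not commit to levels.** This stands. The endpoint text fixes neither scale nor time point. A reader might infer that a DM difference on treatment will be reported as a different response to vorapaxar, but the documents never say so. The supportable statement is that it could be mistaken for one, and that nothing in the plan prevents this.

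**ANCOVA is planned.** This also stands, and it rules out the larger figures. An unadjusted t test of levels would give p<0.05 in about 29%, 62% and 81% of trials at offsets of 5, 8 and 10. A reader might take these as the plan's error rates. They are not, because between-group comparisons are assigned to ANCOVA. The safeguard is only partial, though: the covariate depends on a significance test, and even constant adjustment leaves d(1 − r) in non-randomised cohorts.

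**Separate non-inferiority verdicts may disagree by chance.** With identical truth and 80% power in each cohort, the chance is 2 × 0.8 × 0.2 = 32%. That holds only without within-patient correlation. Both regimens are measured in the same patients, and at correlation 0.5 it falls to about 5%. No section says that discordant verdicts would be read as a DM difference.

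**The change score is not a cure-all.** This stands. The 5% needs an additive offset (step 6), and a clear answer needs a difference of about 7.5 to 11.5 points. Applying three contrasts to at least nine readouts before the TEG parameters would mean 27 or more tests, so the contrast needs one main readout.

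**On-treatment reactivity in DM is a legitimate question, and this is a pilot-type study.** Both are true. They support keeping the level comparisons and limit the weight of the point; they do not supply the missing contrast.

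**Conclusion.** The point holds as a gap in a secondary objective. The documents ask about a difference in drug effect between DM and non-DM patients, but no planned analysis estimates it. With equal additive drug effects and the assumed offsets and correlations, the plan's covariate rule would give a significant cohort difference in about 13% to 51% of trials, against about 5% for the difference in change. The range rests on offsets that the documents do not give: the Background supplies a direction but no size. The 5% rests on an additive effect.

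The documents do not support the stronger conclusion that the trial will misreport a DM difference as a drug effect. The primary within-patient comparison of the two vorapaxar regimens is unaffected. The change is worth making, because it needs only data already planned and answers the question that the rationale poses.

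**What to change.** In Statistical analysis plan:

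- Name the between-cohort difference in within-patient change (equivalently, the cohort-by-visit interaction), with 95% CI, as the analysis of the DM versus non-DM objective. Specify triple therapy minus baseline, dual therapy minus baseline, and dual minus triple.
- Make CAT-induced MPA the main readout for this contrast and label the other readouts exploratory.
- Keep DM versus non-DM comparisons of levels at each visit as description.
- Add a relative scale (log or percent change) as a sensitivity analysis, and say that a conclusion depending on the scale will be reported as such.
- State that differences between cohorts will not be inferred from the separate non-inferiority verdicts.

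A pooled 56-patient dual-minus-triple estimate, stratified by cohort, is optional and does not bear on the DM question.

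**Cost.** SAP wording and an extra contrast; no new patients, visits or samples. The change contrast is noisier than the level contrast if the within-patient correlation is below 0.5 (detectable difference 11.5 against 9.7 points at 0.3), and its result depends on the scale.

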### Statistical analysis plan

Categorical variables will be expressed as frequencies and percentages. Continuous variables will be presented as mean ± SD or median [IQR]. Continuous variables will be analyzed for normal distribution with the Kolmogorov-Smirnov test. Comparisons between categorical variables will be performed using two-tailed Fisher's exact test or the Pearson's chi-square test. Student's t test, Mann-Whitney U-test and Wilcoxon test will be used to compare continuous variables when appropriate. An analysis of covariance (ANCOVA) method with a general linear model, using baseline variables significantly different between groups as covariates, will be used to evaluate the overall difference between groups and all between-groups comparisons, in line with other PD studies [25]. Student's t test or Wilcoxon test will be used to evaluate intragroup comparisons. Non-inferiority will be assessed using a 95% CI of the difference in mean MA between vorapaxar plus prasugrel/ticagrelor and vorapaxar plus DAPT.

A p-value of <0.025 will be considered to be statistically significant for the non-inferiority analysis. A 2-tailed p value of < 0.05 is considered to indicate a statistically significant difference for all the other analyses performed. Statistical analysis will be performed by our group using SPSS v22.0 software (SPSS Inc. Chicago, IL).

## **Publication Strategy/Additional Information**

Study subjects will be identified first (months 1-16): we expect to enroll 4 subjects monthly and complete enrollment in 16 months (total: 64 subjects enrolled). Months 17-18 will be implied for statistical analysis and months 19-20 for manuscript preparation. We intend to present data at a major scientific meeting at completion of the study.

We anticipate no major problems with the described protocol since the approach is a straight forward prospective study and is based on well-established methods. However, since there is limited experience with vorapaxar to define platelet function, variability may be higher than expected and we cannot currently perform a detailed sample size calculation. We anticipate adding this to the protocol after inclusion of the study population has been completed. If the sample size after one year is estimated to be too small, additional patients will be included. This approach is in agreement with recommendations for pilot investigations [28].

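### The plan states a sample size calculation, then says a detailed one cannot yet be done, and it lets patients be added after one year with no statistic, reference number or maximum

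*Combined protocol and SAP*

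**What the plan says.** Study endpoints and sample size calculation sets a non-inferiority comparison of CAT-induced maximal platelet aggregation (MPA) between vorapaxar plus clopidogrel and vorapaxar plus dual antiplatelet therapy. The hypothesis covers both the diabetes and the non-diabetes cohort. The inputs are a true difference of 0, a margin of 10%, 80% power and alpha 0.025, with "a common standard deviation of 13%, a sample size of 28 patients per group". It continues: "a total of 56 patients with valid primary end point data will need to be included". On losses it says: "Assuming up to 40% rate of invalid results due to haemolysis or drop-out, up to 79 patients will need to be enrolled". The SD is attributed to earlier data on vorapaxar added to dual therapy.

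Publication Strategy/Additional Information plans 4 patients a month for 16 months, 64 in total. It warns that "variability may be higher than expected" and states "we cannot currently perform a detailed sample size calculation". On timing it says: "We anticipate adding this to the protocol after inclusion of the study population has been completed". It then adds: "If the sample size after one year is estimated to be too small, additional patients will be included".

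The Statistical analysis plan section tests non-inferiority at 0.025. It describes no interim look and no re-estimation of sample size.

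**The concern.** There are three difficulties.

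- One section supplies a calculation with its inputs, and the other says a detailed one is not yet possible. A reader cannot tell which governs.
- The order does not work. The number is judged after one year, but the calculation is due only once inclusion has ended, at month 16. A calculation added after inclusion cannot justify the number included.
- The provision to add patients is open. It does not say what is estimated, what number counts as sufficient, or how far enrolment may go.

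All patients follow the same open sequence of regimens and the investigators' own group does the analysis, so the treatment difference is within reach at the review. If patients were added, nobody could show afterwards whether the reason was a larger SD, too few valid samples or an unfavourable difference.

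**Working it through.** **1. The plan's own figure.** Inputs from the sample size section: margin 10, SD 13, difference 0, one-sided alpha 0.025, power 80%. For two independent groups, n = 2 × [13 × (1.960 + 0.842) / 10]² = 26.5, so 27 per group. With the noncentral t, 27 per group gives 79.2% power and 28 gives 80.7%. The stated 28 is the smallest adequate number, and 2 × 28 = 56. The calculation exists and reproduces.

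**2. What it leaves out.** Each patient receives both regimens in turn, so the relevant SD is that of the within-patient difference, 13 × √[2(1 − r)]. The documents give no correlation r. For 28 pairs:

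| r (assumed) | SD of difference | Power |
|---|---|---|
| 0 | 18.4 | 79% |
| 0.25 | 15.9 | 89% |
| 0.5 | 13.0 | 97.5% |

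Twenty-eight pairs keep 80% power up to an SD of the difference of 18.2. That is a common SD of 12.9 at r = 0 or 18.2 at r = 0.5.

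**3. Timing.** At 4 a month, month 12 has 48 enrolled, and enrolment ends at month 16. Patients enrolled by month 10 (40) would have finished the roughly 60 days of treatment. With an even split that is 20 per cohort, or 12 after a 40% loss.

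**4. Which number is the reference?** Here 40% is read as the fraction lost.

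- 64 × 0.6 = 38.4, about 38 evaluable (19 per cohort).
- 79 × 0.6 = 47.4, about 47 evaluable.
- 64 enrolled gives 56 only if loss is at most 1 − 56/64 = 12.5%.
- 56 / 0.6 = 93.3, so 94 enrolled would be needed. The plan's 79 matches 56 × 1.4 = 78.4.

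At that ceiling the sample could be judged too small with no variability problem at all.

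**5. Error if the result drove the decision.** Assumptions: paired data, SD of the difference 13, true difference equal to the margin. There is one look, and the sample is extended from 28 to a larger size if the look p-value exceeds 0.025, 0.1, 0.2 or 0.5. One final test is made at 0.025. One-sided error, as the range over those four cut-offs (1,000,000 simulated trials):

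| Look (per cohort) | Extend to 42 | Extend to 56 |
|---|---|---|
| 12 | 2.6-2.9% | 2.7-3.1% |
| 20 | 2.5-3.1% | 2.6-3.4% |

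**6. Error if only the SD drove it.** The floor is 28, the maximum 34, 40 or 56, and the true SD of the difference 13 or 18.4 (400,000 trials). Error is 2.5-2.7%. At 18.4, power is 83-85% and the mean number is 30-33 per cohort.

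**The case against.** The strongest defence is that the two sections are compatible. The first would be provisional: it admits there are no preliminary data in this setting and calls its margin arbitrary. The second would promise a more detailed calculation once variability is known, and both cite guidance on pilot studies. Part of this stands. The stated calculation omits the within-patient correlation, so it is not complete, and the warning about variability is honest and should stay. The defence does not repair the order of events, and a pilot that makes a formal non-inferiority test still has to show how its number was fixed.

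It can also be said that variability is the only motive given, so a review of the SD is implied. That is a fair reading of intent, but no estimator or threshold follows, and nothing keeps the difference out of view.

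A reader might infer more than the documents support:

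- That the investigators plan to extend on the observed result, or that the error rate is badly inflated. Nothing states such a plan. The simulated excess is below one percentage point, although repeated extensions were not simulated.
- That 64 enrolled must fall short of 56 evaluable. The 40% is a ceiling, so 38 and 47 are worst-case yields on one reading of it.
- That up to 79 is a cap on the added patients. It is the target inflated for losses, and the provision does not refer to it.

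**Conclusion.** The point holds, and its weight is minor to moderate. The plan states a reproducible calculation and elsewhere says a detailed one cannot yet be done. It places the review of the number before the promised calculation, and it leaves the decision to add patients without a statistic, reference number or maximum. The effect on error is modest: about 2.5-3.4% one-sided if the result drove a single extension, and 2.5-2.7% if only the SD did. Those figures rest on assumed look sizes, cut-offs and maxima, not on rules in the plan. The main harm is to credibility, because the final number could not be shown to have been chosen independently of the result.

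**What to change.** In Publication Strategy/Additional Information, replace the statements that the calculation cannot be done and will follow inclusion with a reference to the sample size section. Keep the caution that the SD is uncertain. Name 28 evaluable patients per cohort as the reference number. Reconcile 64 with 79 and state the evaluable number expected. Then choose one of two courses.

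- **Drop** the provision to add patients for variability.
- **Limit it** to one review, for example: *At one year the SD of the within-patient difference in CAT-induced MPA will be estimated once in each cohort. The mean difference and its confidence interval will not be computed. The number will be recalculated with margin, power and alpha unchanged. It will not fall below 28 evaluable patients per cohort or exceed a maximum fixed before the review. No non-inferiority claim will be made at this review.*

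The floor matters because an SD of the difference of 13 would need only 16 pairs. No maximum guarantees 80% power: the 95% limits of an SD run from 0.71 to 1.70 times the estimate with 12 patients, and from 0.76 to 1.46 times with 20.

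Under either course, state separately that replacing invalid samples, up to 28 evaluable per cohort, depends only on the count of valid samples.

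**Cost.** Dropping the provision is a wording change, but it gives up protection against higher variability. At the 40% ceiling, 64 enrolled would still fall short of 56 unless invalid samples are replaced or the expected precision is restated. Enrolment at that ceiling, against the planned 64 and at 4 a month:

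| Evaluable per cohort | Enrolled | More than 64 | Extra months |
|---|---|---|---|
| 28 | 56 / 0.6 ≈ 94 | 30 | 7.5 |
| 34 (example maximum) | 68 / 0.6 ≈ 114 | 50 | 12.5 |
| 40 (example maximum) | 80 / 0.6 ≈ 134 | 70 | 17.5 |

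Lower loss needs fewer patients. Any of these would move the end of enrolment and the analysis planned for months 17-18.
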